ANC	absolute neutrophil count
AUC	Area under the curve
BMI	Body mass index
CHC	Chronic hepatitis C
DAA	Direct acting antiviral
ECG	Electrocardiogram
ESA	Erythropoiesis stimulating agent
ETR	end of treatment response: <LLOQ HCV RNA at the end of treatment
EVR	early virologic response: <LLOQ HCV RNA or 2-log decline at Week 12 (partial EVR)
FDA	Food and Drug Administration
FDC	Fixed dose combination
G-CSF	granulocyte colony stimulating factor
GT-1, -2, and -3	Genotype 1, 2, and 3
HBV	hepatitis B virus
HCV	hepatitis C virus
Hgb	hemoglobin
HIV	human immunodeficiency virus
IL28B	Interleukin 28B
IFN	interferon
IRB	Institutional Review Board
ISG	interferon-stimulated gene
LDV	Ledipasvir
LI	Lead investigator
LOD	Level of detection
LLOQ	Lower Level of quantification
MELD	Model for End-Stage Liver Disease
NIAID	National Institute of Allergy and Infectious Diseases
NIH	National Institutes of Health
PBMC	peripheral blood mononuclear cell
pegIFN	Pegylated Interferon
PI	principal investigator
sofosbuvir	sofosbuvir
QWBA	quantitative whole-body autoradiography
RBV	ribavirin
RVR	Rapid virologic response; <LLOQ HCV RNA at Week 4
SAE	Serious adverse events
SOC	Standard of care
SOF	Sofosbuvir
SVR	sustained virologic response <LLOQ HCV RNA at 24 weeks (or 6 months) after the end of treatment
TVR	Telaprevir

PROTOCOL SUMMARY

Full Title:	A Retrospective/Prospective Cohort Study to Assess Safety, Tolerability, and Efficacy of Sofosbuvir based Direct Acting Antiviral (DAA) therapy for Hepatitis C Treatment in HIV/HCV Coinfected Subjects Pre or Post Liver Transplant
Short Title:	Sofosbuvir based DAA therapy in HIV/HCV coinfected pre or post liver transplant
Study Name:	STOP-CO
DAIDS ES #:	12044
Clinical Phase:	Phase IV
Sample Size:	10+ prospective (up to 20) 40+ retrospective
Accrual Period:	12 months
Study Population:	HIV+ Adults with decompensated liver disease pre or post liver transplant with chronic hepatitis C virus (HCV) infection
Participating Sites:	Enrolling Centers: University of California, San Francisco, Mt. Sinai Medical Center, Columbia University, and University of Pennsylvania, University of Maryland, Georgetown University, Johns Hopkins University; Collaborating Center: NIH Clinical Center.
Study Design:	Retrospective/Prospective, open-label study using sofosbuvir based DAA therapy to treat HIV/HCV coinfected pre or post liver transplant participants

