3.0 STUDY DESCRIPTION

Approximately fifty HIV/HCV coinfecte patients with decompensated liver disease will be enrolled in the study. Ten (up to twenty) subjects will be treated with FDC SOF/LDV pre or post liver transplant and followed prospectively. Forty + subjects will be enrolled retrospectively with the intent to capture all patients who have been exposed to sofosbuvir based DAA therapies at participating sites since 1/2014, and to mirror the population being enrolled prospectively.

In addition, participants in the retrospective arm will be contacted to consent to one prospective study visit for liver staging to determine rates of reversal of decompensation, reversal of cirrhosis and improvements in graft survival post treatment, and for future contact by the NIH Clinical Center to assess longer term outcomes when this study ends.

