4 STATISTICAL ANALYSIS

4.1 Sample Size Requirements

The sample size of 50 was chosen for 3 reasons:

1. This is an achievable sample size given the number of known pool of HCV/HIV coinfected liver transplant candidates and recipients at the participating study sites and the available time for recruitment. This sample size will also represent the largest experience with interferon- and ribavirin-free therapy in this specific population. In terms of the primary efficacy endpoint, combined (pre and post-transplant) and separate analyses of SVR₁₂ will be estimated. Table 1 shows the width of a 95% exact confidence interval for the probability of SVR₁₂ as a function of the number of SVRs in a sample size of 50. For instance, if all 50 subjects have sustained virologic response, we can be 95% confident that the true SVR probability is between 0.929 and 1.

Table 1: SVR₁₂ Confidence Interval Table

50	48	46	44	42	40
0.929-1	0.863-0.995	0.808-0.978	0.757-0.955	0.709-0.928	0.663-0.900

Exact 95% confidence interval if the number of SVRs out of 25 is as shown in row 1.

2. A sample size of 50 (pre and post-transplant) is sufficient to address the safety endpoints. If the true event probability is 5% or more, there is about a 92% chance of observing at least one such adverse event (Table 2). Consequently, if no one has a given type of AE, we can be confident that its true probability is under 5%. This trial will provide preliminary evidence on the safety and efficacy of FDC in pre or post liver transplant HIV/HCV coinfected subjects.

Table 2: Adverse Event Probability Table

.01	.05	.10	.15
39%	92%	99.5%	99.97%

For AE probabilities shown in row 1, row 2 gives the probabilities of observing at least 1 participant with the AE among 50 total participants.

3. A sample size of 50 is adequate to support the mechanistic virologic and immunologic studies.

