10.6 Reporting Procedures: Retrospective Arm

Adverse event and safety monitoring is not required for the retrospective arm since the retrospective arm only involves data collection and elastography for those who consent. Elastography is ultrasound based and is without adverse events. However, sites will be asked to record data on historical adverse events identified in the medical record for data analysis (hospitalizations during treatment with DAA therapy, anemia requiring transfusion or EPO during treatment with DAA therapy, and death) but the retrospective arm participants are exempt from ongoing safety monitoring.

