12 MECHANISTIC STUDIES: PROSPECTIVE ARM

Viral Kinetics

Samples from Days 0, week 4, and end of treatment (EOT) will be used to assess HCV viral load levels.

HCV Virologic Studies

Full length HCV genome pyro sequencing may be performed using the protocol as described and compared for variability of sequences [45].

rs12979860 (IL28B) Genetic Variant

IL28B genetic variants have been shown to predict HCV treatment induced clearance. The IL28B assay is a real-time PCR assay that utilizes 5-prime nuclease activity of a thermostable polymerase and unique primers and SNP-specific probes to determine the genotype. Test results will not be used as inclusion or exclusion criteria, or to randomize subjects into treatment groups.

Immune Responses to HCV and HIV

Both humoral and cellular immunity against HCV and HIV will be estimated before and during treatment to assess the effect of HCV treatment on host immune response against HCV. We may also perform multiplex PCR assays to detect ISGs before and during treatment.

HCV Genotypic and Phenotypic Resistance Monitoring

Serum samples for genotypic and phenotypic monitoring will be collected

Resistance monitoring will be completed in all subjects who received study drug and were virologic failures as defined.

Subjects who are determined by sequencing and phenotypic analysis to have had mutations leading to SOF resistance will be requested to return at 12 week intervals for up to 48 weeks after the last dose of study drug to determine the time for the resistant virus to return to background levels.

RNA Extraction from liver tissue

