18 STORED SAMPLES AND FUTURE RESEARCH: PROSPECTIVE ARM

Extra blood and tissue samples will be stored using a code name that only the study team can link back to the participants. These samples will be stored for future research. Other investigators may want to pursue additional research using these stored samples. If so, the study team will seek IRB approval prior to sharing of any samples. After approval, the study team may send these samples to them, along with the coded label. Investigators will use stored samples only for research. At the completion of the protocol, samples and data will either be destroyed, or after IRB approval, will be transferred to another existing protocol. The IRB will be notified in writing of any loss or destruction of stored samples.

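### Section 4.1 justifies the sample-dependent mechanistic studies with 50 patients, but only the 10 to 20 prospective participants can supply them

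*Combined protocol and SAP*

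**What the plan says.** Section 4.1 gives three reasons for a sample size of 50. The third is one sentence: "A sample size of 50 is adequate to support the mechanistic virologic and immunologic studies". No effect size, variance, power or precision target accompanies it.

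The Protocol Summary gives the sample size as "10+ prospective (up to 20) 40+ retrospective". Section 3.0 says "Ten (up to twenty) subjects will be treated with FDC SOF/LDV pre or post liver transplant and followed prospectively", and that forty or more further "subjects will be enrolled retrospectively with the intent to capture all patients who have been exposed to sofosbuvir based DAA therapies".

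Section 12, which describes the mechanistic work, is headed "MECHANISTIC STUDIES: PROSPECTIVE ARM". Section 18 is headed "STORED SAMPLES AND FUTURE RESEARCH: PROSPECTIVE ARM". Section 10.6 says that "the retrospective arm only involves data collection and elastography for those who consent".

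**The concern.** One of the three stated reasons for the sample size relies on a number of patients that the design does not provide for that purpose. Forty or more of the 50 contribute chart data and, with consent, one liver-staging visit. They give no blood or tissue for research.

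Section 3.3.2 lists secondary endpoints that set responders against non-responders: interferon-stimulated gene response, host genetic and proteomic factors, and immunologic correlates, by RVR and SVR. Someone who plans or reads those analyses from section 4.1 alone would take the base to be 50. If SVR is high, the contrasts by SVR status depend on very few non-SVR patients, and the size of the arm then decides whether there is a comparison group at all.

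**Working it through.** **1. What the 50 is.** The arms add to it: 10 + 40 = 50. The other figures in section 4.1 also use 50.
- Table 1, exact Clopper-Pearson limits: with all 50 responding, the lower limit is 0.025^(1/50) = 0.929, as stated. The other five entries reproduce at n = 50 too (the footnote says 25, but the entries are those for 50).
- Table 2, 1 − (1 − p)^50: 39.5%, 92.3%, 99.5% and 99.97% for p = 0.01, 0.05, 0.10 and 0.15. The plan states 39%, 92%, 99.5% and 99.97%.

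Reason 3 has no figure to reproduce, because it gives no inputs.

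**2. Which arm supplies the mechanistic work.**
- Section 12 (prospective by its heading) holds the viral kinetics, sequencing, IL28B, immune-response, resistance and explant RNA work.
- Section 2.2 marks objectives 5 (host factors) and 6 (interferon-stimulated genes) as prospective only.
- The section 11.1 schedule has rows for immunology blood, Paxgene DNA and RNA, HLA, IL28B, explant tissue and stored blood. The retrospective schedules in 11.2 and 11.3 have none of these for research; they record chart data and one liver-staging visit.
- Exception: sections 6.3 and 11.2 record retrospective HCV RNA at Day 0, week 4 and end of treatment. Section 12 uses the same time points for viral kinetics.

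**3. Available number.** 10/50 = 20% and 20/50 = 40%. If 20 prospective patients join 40 retrospective ones, the share is 20/60 = 33%. Some pieces are smaller still: the interferon-stimulated gene endpoint in section 3.3.2 concerns subjects treated for 12 weeks, resistance monitoring covers virologic failures, and explant RNA covers patients who reach SVR and are later transplanted.

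**4. Illustration by SVR status.** The protocol states no planning SVR rate. I assume 80%, 90% and 95%, within the 80% (40/50) to 100% (50/50) span of Table 1. Expected non-SVR patients = n(1 − p); chance of none = p^n.

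| n | Expected non-SVR at SVR 80% / 90% / 95% | Chance of no non-SVR patient at SVR 80% / 90% / 95% |
|---|---|---|
| 10 | 2 / 1 / 0.5 | 11% / 35% / 60% |
| 20 | 4 / 2 / 1 | 1% / 12% / 36% |
| 50 | 10 / 5 / 2.5 | <0.1% / 0.5% / 8% |

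**5. Illustration for two continuous measures.** For an assumed observed correlation of 0.5, the Fisher z 95% interval, tanh(0.549 ± 1.96/√(n − 3)), is 0.26 to 0.68 at n = 50, 0.07 to 0.77 at n = 20, and −0.19 to 0.86 at n = 10. The 0.5 is my choice, and the calculation does not apply to responder contrasts.

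**The case against.** The strongest reply has four parts.

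- **Viral kinetics can use both arms.** Objectives 1 (kinetics) and 8 (resistance) are not marked prospective only, and charted HCV RNA exists at the kinetics time points. This stands for viral-load decline, so a reader who inferred that all virologic work is limited to 10 to 20 patients would go too far. It does not extend to sequencing or resistance testing, because the retrospective schedules provide no specimen for them.
- **Inadequacy is not shown.** A reader might infer that 10 to 20 patients are too few for the mechanistic studies. The documents do not support that: without a target, neither 50 nor 10 to 20 can be called adequate or inadequate. This stands. The illustrations rest on assumed values, and scarcity of SVR failures says nothing about contrasts by RVR, whose split is unknown. High SVR also limits a sample of 50, with only 5 non-SVR patients expected at 90%.
- **The protocol signals the limit elsewhere.** The labels on objectives 5 and 6, the Section 12 heading, the description of the SOF/LDV work as a pilot (section 1.1) and the caution about multivariate models (section 4.4.2) make misreading less likely. They lessen the consequence, but none of them corrects reason 3.
- **Nothing is miscalculated.** True. This is an inconsistency between sections. The planned SVR12 interval in section 4.4.1 does not depend on reason 3, so it gives no ground to question that analysis.

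**Conclusion.** Reason 3 is wrong as written for the sample-dependent mechanistic studies. The number available is 10, at most 20, which is 20% to 40% of the 50 cited. That conclusion needs only the stated arm sizes and the stated scope of each arm.

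The practical effect is less certain. Under assumed SVR rates of 80% to 95%, 0.5 to 4 non-SVR patients are expected in the mechanistic set, against 2.5 to 10 if all 50 contributed. At 90% to 95%, the chance of having none is 35% to 60% with 10 participants and 12% to 36% with 20. The point is confined to exploratory secondary work and to one sentence of the sample size justification.

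**What to change.** Reword reason 3 to say that the sample-dependent mechanistic studies will include the 10 to 20 prospective participants and are exploratory and descriptive. Remove the statement that 50 is adequate for them. Say separately whether viral-load decline from recorded HCV RNA will be described in both arms, so that the new wording does not conflict with objective 1.

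Optionally, state that analyses by SVR status will show individual values when there are fewer than about five non-SVR patients. That threshold is a matter of preference; the documents do not require it.

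The change is to wording only: enrolment, procedures and the primary analysis stay as they are. The cost is that a stated figure becomes less favourable and the sample size of 50 then rests on the other two reasons.

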4.1.1 Primary Endpoint

The primary efficacy endpoint is SVR₁₂ (HCV RNA < LLOQ 12 weeks after cessation of therapy).

4.1.2 Secondary Endpoints

Secondary efficacy endpoints include: HCV RNA < LLOQ at 4 and 24 weeks after discontinuation of therapy (SVR₄ and SVR₂₄); viral breakthrough; and relapse.

4.1.3 Safety Endpoints

The primary safety endpoint is any AE leading to permanent discontinuation of study drug(s).

4.1.4 Other Endpoints of Interest

Additional efficacy evaluations may include HCV RNA change from Day 0; ALT normalization; and viral kinetic parameters.

4.2 Analysis Populations

Safety and efficacy will be evaluated using the safety population.

4.2.1 Efficacy Population

The primary analysis population for efficacy analysis will be defined as all participants who received at least one dose of study drug.

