2.0 OBJECTIVES

2.1 Primary Objectives

1. To assess the safety, tolerability, and efficacy of sofosbuvir based DAA therapy for 12 – 24 weeks in HIV/HCV coinfecting participants pre- and post-liver transplant.
2. To assess the safety, tolerability, and efficacy of a fixed dose combination (FDC) of sofosbuvir and ledipasvir (SOF/LDV) for 12 to 24 weeks in HIV/HCV coinfecting participants pre or post liver transplant.

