4.4 Efficacy Analyses

4.4.1 Primary Analysis

The primary efficacy endpoint is SVR₁₂ (HCV RNA <LLOQ 12 weeks after cessation of therapy.)

There is no active comparator group for this study (as in most clinical trials with all oral therapies in these populations).

In the primary efficacy analysis, an exact Clopper-Pearson 95% confidence interval will be computed for the SVR₁₂ rate.

The primary analysis will be performed after all enrolled subjects have been followed through 12 weeks post-treatment or discontinued from study.

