9 EVALUATION OF SAFETY

All enrolled subjects who have received SOF/LDV will be evaluated for safety. Safety will be assessed by physical examination, vital signs, hematology, and chemistries. The severity of signs, symptoms, and AEs will be determined by using the 2014 DAIDS Table for Grading the Severity of Adult and Pediatric Adverse Events, with edits made to allow for clinical center normal values.

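### Both analysis sets rest on a term that fits only the 10–20 prospective patients, and the n=50 precision does not carry over to the SOF/LDV objective or to adverse events in general

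*Combined protocol and SAP*

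**What the plan says.** Section 3.0 describes about fifty patients: ten, or up to twenty, treated prospectively with SOF/LDV, and forty or more enrolled retrospectively after exposure to any sofosbuvir-based DAA. Section 2.1 sets two primary objectives, the first on sofosbuvir-based DAA therapy and the second on fixed-dose SOF/LDV.

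The efficacy population (4.2.1) is "all participants who received at least one dose of study drug", and the safety population (4.2.2) has the same criterion. Section 4.4.1 then specifies one analysis: "an exact Clopper-Pearson 95% confidence interval will be computed for the SVR₁₂ rate". Section 9 adds a further description for safety: "All enrolled subjects who have received SOF/LDV will be evaluated for safety".

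The precision statements in section 4.1 all use 50. For efficacy: "if all 50 subjects have sustained virologic response, we can be 95% confident that the true SVR probability is between 0.929 and 1". For safety: "If the true event probability is 5% or more, there is about a 92% chance of observing at least one such adverse event". The same section goes on to say that the trial will give preliminary evidence on the safety and efficacy of the fixed-dose combination.

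**The concern.** *Study drug* is never formally defined. Section 8, whose title limits it to the prospective arm, uses it for the SOF/LDV distributed through the trial's investigational pharmacy, and section 12, limited in the same way, also speaks of subjects who received study drug. Treatment in the retrospective arm is called sofosbuvir-based DAA therapy, or simply DAA therapy (sections 3.1, 5.1, 6.3 and 10.6). Taken at their word, 4.2.1 and 4.2.2 therefore leave out the forty or more retrospective patients who make up most of the 50 in Tables 1 and 2.

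This matters because the study has no comparator and no hypothesis test: the primary result is a proportion and its interval, so the denominator largely determines the result. If the set is not fixed beforehand, it can be chosen after the responses are known. The tables would also tell a reader that the SOF/LDV question will be answered with a precision that the assured number of SOF/LDV patients cannot give.

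**Working it through.** **Inputs.** Exact two-sided 95% Clopper-Pearson interval (4.4.1); n=50 for both tables (4.1); prospective arm 10–20, retrospective arm 40 or more (3.0).

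**Formulas.** For x responders out of n, the lower limit is the 0.025 quantile of Beta(x, n−x+1) and the upper limit is the 0.975 quantile of Beta(x+1, n−x). When x = n the lower limit is 0.025^(1/n) and the upper limit is 1. The chance of at least one event at true rate p is 1−(1−p)^n. After zero events the one-sided 95% upper limit is 1−0.05^(1/n).

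**The plan's own figures.** At n=50, 50, 48, 46, 44, 42 and 40 responders give 0.929–1, 0.863–0.995, 0.808–0.978, 0.757–0.955, 0.709–0.928 and 0.663–0.900, which is Table 1. True rates of 1%, 5%, 10% and 15% give 39%, 92%, 99.5% and 99.97%, which is Table 2. The note under Table 1 that refers to 25 patients is a labelling slip: 25/25 would give 0.863–1.

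**The same quantities at the assured SOF/LDV numbers.** For example, 0.025^(1/20) = 0.832 and 0.025^(1/10) = 0.692; 1−0.95^20 = 64.2% and 1−0.95^10 = 40.1%.

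| n | All reach SVR12 | 80% reach SVR12 | At least one event, true rate 5% | At least one event, true rate 10% | Upper limit after zero events |
|---|---|---|---|---|---|
| 50 | 0.929–1 | 0.663–0.900 | 92.3% | 99.5% | 5.8% |
| 20 | 0.832–1 | 0.563–0.943 | 64.2% | 87.8% | 13.9% |
| 10 | 0.692–1 | 0.444–0.975 | 40.1% | 65.1% | 25.9% |

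**Which n belongs to which question.**
- *Literal reading of 4.2:* 10–20 patients. Neither table applies.
- *Pooled reading:* at least 10+40 = 50 patients. Table 1 fits the combined estimate for objective 1. It does not describe objective 2, because retrospective patients may have had any sofosbuvir-based regimen.
- *SOF/LDV from any source:* somewhere between 10 and 60 or more. The protocol does not say how many retrospective patients received SOF/LDV.

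**Table 2 on the pooled reading.** Section 10.6 requires no adverse-event monitoring in the retrospective arm and asks only for hospitalization, anemia requiring transfusion or EPO, and death; section 3.1 adds discontinuation rates. For any other event type, 50 patients are not under observation, so the 92% does not apply. Section 5.1 also admits only retrospective patients who survived at least 12 weeks from the start of treatment, so earlier deaths cannot appear in that arm.

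**The case against.** The best reply is that pooling was plainly meant. Section 3.0 counts both arms as enrolled, the note to Table 2 refers to 50 total participants, the primary analysis in 4.4.1 waits for all enrolled subjects, and section 10.6 has retrospective events recorded for analysis. This is a pilot that estimates a proportion, its size is justified first by feasibility, and 4.4.2 leaves efficacy details to a statistical analysis plan. Much of this stands. A reader might infer that n=50 belongs to no analysis set at all; the documents do not support that, because the term is undefined and a pooled set would fit Table 1. But 4.2 already fixes the population in words that do not produce the pooled set, and nothing supplied corrects them.

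Three other inferences are tempting and should not be drawn.
- *That 4.1 claims n=50 precision for the separate pre- and post-transplant estimates.* It promises those estimates but ties Table 1 only to a sample of 50.
- *That objective 2 is confined to the prospective arm.* Secondary objectives 5 and 6 carry that restriction; primary objective 2 does not, and section 9 names no arm. So 10–20 is the assured number, not an established denominator.
- *That 0.692 fails against the early response of over 70% cited for sofosbuvir plus ribavirin after transplant.* Section 1.1 gives that figure as a response four weeks after treatment with a different regimen, and the plan uses it as no benchmark.

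**Conclusion.** Wrong as written. On either main reading, a precision figure stated in section 4.1 is not delivered. Literally, the sets hold 10–20 patients and miss both tables. Pooled, Table 1 is right for objective 1, but objective 2 has no stated precision and Table 2 is too broad. For the assured SOF/LDV patients, the lower limit with complete response falls from 0.929 to between 0.832 and 0.692, and the chance of seeing an event with a true 5% rate falls from 92% to between 64% and 40%.

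This rests on two things: that *study drug* means the prospective arm's SOF/LDV, which is inferred from consistent use and not from a definition; and that no retrospective SOF/LDV recipients are counted, since their number is not given. If many were counted, objective 2 would be more precise than shown here, but the limit on event types would remain. The arithmetic of both tables is correct for n=50.

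**What to change.** - **Set 1, objective 1.** Reword 4.2 to cover all patients in both arms with at least one dose of their index sofosbuvir-based course. Report it pooled and by arm, because retrospective entry requires 12-week survival and section 3.1 defines efficacy there as undetectable HCV RNA at 12 weeks or later, whereas 3.3.1 uses a value below LLOQ at 12 weeks.
- **Set 2, objective 2.** SOF/LDV recipients, with the prospective arm as the prespecified estimate and an explicit statement of whether retrospective SOF/LDV recipients are added.
- **Analysis.** In 4.4.1, compute one Clopper-Pearson interval per set.
- **Tables.** Add n=10 and n=20 rows to Tables 1 and 2, label n=50 as the pooled set only, and limit Table 2 at n=50 to the event types abstracted in both arms.

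The change is to wording and tables and needs no new data collection. Its cost is that the stated precision for objective 2 and for adverse-event detection becomes less favourable.
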